5.5.2 Contraception

Pembrolizumab may have adverse effects on a fetus in utero. Furthermore, it is not known if pembrolizumab has transient adverse effects on the composition of sperm. Non-pregnant, non-breast-feeding women may be enrolled if they are willing to use 2 methods of birth control or are considered highly unlikely to conceive. Highly unlikely to conceive is defined as 1) surgically sterilized, or 2) postmenopausal (a woman who is ≥ 45 years of age and has not had menses for greater than 1 year will be considered postmenopausal), or 3) not heterosexually active for the duration of the study. The two birth control methods can be either two barrier

methods or a barrier method plus a hormonal method to prevent pregnancy. Subjects should start using birth control from study Visit 1 throughout the study period up to 120 days after the last dose of study therapy.

The following are considered adequate barrier methods of contraception: diaphragm, condom (by the partner), copper intrauterine device, sponge, or spermicide. Appropriate hormonal contraceptives will include any registered and marketed contraceptive agent that contains an estrogen and/or a progestational agent (including oral, subcutaneous, intrauterine, or intramuscular agents).

Subjects should be informed that taking the study medication may involve unknown risks to the fetus (unborn baby) if pregnancy were to occur during the study. In order to participate in the study they must adhere to the contraception requirement (described above) for the duration of the study and during the follow-up period defined in section 8.6-Reporting of Pregnancy and Lactation to Merck. If there is any question that a subject will not reliably comply with the requirements for contraception, that subject should not be entered into the study.

5.5.3 Use in Pregnancy

If a subject inadvertently becomes pregnant while on treatment with pembrolizumab, the subject will immediately be removed from the study. The site will contact the subject at least monthly and document the subject's status until the pregnancy has been completed or terminated. The outcome of the pregnancy will be reported to the Sponsor and to Merck without delay and within 24 hours to the Sponsor and within 2 working days to Merck if the outcome is a serious adverse experience (e.g., death, abortion, congenital anomaly, or other disabling or life-threatening complication to the mother or newborn).

The study investigator will make every effort to obtain permission to follow the outcome of the pregnancy and report the condition of the fetus or newborn to the Sponsor. If a male subject impregnates his female partner the study personnel at the site must be informed immediately and the pregnancy reported to the Sponsor and to Merck and followed as described above and in Section 8.6.

5.5.4 Use in Nursing Women

It is unknown whether pembrolizumab is excreted in human milk. Since many drugs are excreted in human milk, and because of the potential for serious adverse reactions in the nursing infant, subjects who are breast-feeding are not eligible for enrollment.

5.6 Subject Withdrawal/Discontinuation Criteria

Subjects may withdraw consent at any time for any reason or be dropped from the trial at the discretion of the investigator should any untoward effect occur. In addition, a subject may be withdrawn by the investigator or the Sponsor if enrollment into the trial is inappropriate, the trial plan is violated, or for administrative and/or other safety reasons. Specific details regarding discontinuation or withdrawal are provided in [Section 7.1.4 – Other Procedures](#).

A subject must be discontinued from the trial for any of the following reasons:

- The subject or legal representative (such as a parent or legal guardian) withdraws consent.
- Confirmed radiographic disease progression

Note: For unconfirmed radiographic disease progression, please see [Section 5.2.2](#)

Note: A subject may be granted an exception to continue on treatment with confirmed radiographic progression if clinically stable or clinically improved, please see [Section 7.1.2.6.2](#)

- Unacceptable adverse experiences as described in [Section 5.2.1.2](#)
- Intercurrent illness that prevents further administration of treatment
- Investigator's decision to withdraw the subject
- The subject has a confirmed positive serum pregnancy test
- Noncompliance with trial treatment or procedure requirements
- The subject is lost to follow-up
- Completed 24 months of uninterrupted treatment with pembrolizumab or 35 administrations of study medication, whichever is later.

Note: 24 months of study medication is calculated from the date of first dose. Subjects who stop pembrolizumab after 24 months may be eligible for up to one year of additional study treatment if they progress after stopping study treatment provided they meet the requirements detailed in [Section 7.1.5.5](#)

- Administrative reasons

The End of Treatment and Follow-up visit procedures are listed in [Section 6.0](#) (Study Calendar) and [Section 7.1.5](#) (Visit Requirements). After the end of treatment, each subject will be followed for 30 days for adverse event monitoring (serious adverse events will be collected for 90 days after the end of treatment as described in [Section 8.0](#)). Subjects who discontinue for reasons other than progressive disease will have post-treatment follow-up for disease status until disease progression, initiating a non-study cancer treatment, withdrawing consent or becoming lost to follow-up. After documented disease progression each subject will be followed by telephone for overall survival until death, withdrawal of consent, or the end of the study, whichever occurs first.

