We propose a prospective trial to assess pre- and post-treatment biopsies of patients' metastatic sites with the hypothesis that tumor cytotoxic T cells will be increased with combining pembrolizumab and palliative RT with corresponding improvement in clinical activity. As we will only be radiating a single target lesion in this study population, assessment of response among non-irradiated metastatic sites will serve as a true measure of the abscopal effect. Toxicities are not anticipated to be overlapping for these two modalities, though safety should still be assessed in this early cohort of patients to ensure immune-mediated or radiation-induced toxicities are not exacerbated by the combination. At City of Hope where patients will be solely recruited for this trial, we have extensive experience in the conduct of pre- and post-treatment biopsy studies having completed accrual to a pilot trial of the novel nanopharmaceutical CRLX101 in this disease subset (Clinicaltrials.gov, NCT01612546). We also have a broad gastroesophageal cancer patient population evaluating more than 60 new cases per year due to our institution serving the diverse, multicultural population of the San Gabriel Valley in Los Angeles County. [name], MD, Chair of the Department of Immuno-Oncology, will serve as a collaborating investigator on this study given his laboratory's expertise in translational analyses of tumor/immune/stromal cell interactions.

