5.2.1.2 Dose Modification

Adverse events (both non-serious and serious) associated with pembrolizumab exposure may represent an immunologic etiology. These adverse events may occur shortly after the first dose or several months after the last dose of treatment. Pembrolizumab must be withheld for drug-related toxicities and severe or life-threatening AEs as per [Table 2](#) below. See [Section 5.4.1](#) and Events of Clinical Interest Guidance Document for supportive care guidelines, including use of corticosteroids.

Table 2: Dose Modification Guidelines for Drug-Related Adverse Event

Toxicity	Hold Treatment For Grade	Timing for Restarting Treatment	Discontinue Subject
Diarrhea/Colitis	2-3	Toxicity resolves to Grade 0-1.	Toxicity does not resolve within 12 weeks of last dose or inability to reduce corticosteroid to 10 mg or less of prednisone or equivalent per day within 12 weeks.
	4	Permanently discontinue	Permanently discontinue
AST, ALT, or Increased Bilirubin	2	Toxicity resolves to Grade 0-1	Toxicity does not resolve within 12 weeks of last dose.
	3-4	Permanently discontinue (see exception below) ¹	Permanently discontinue
Type 1 diabetes mellitus (if new onset) or Hyperglycemia	T1DM or 3-4	Hold pembrolizumab for new onset Type 1 diabetes mellitus or Grade 3-4 hyperglycemia associated with evidence of beta cell failure.	Resume pembrolizumab when patients are clinically and metabolically stable.
Hypophysitis	2-3	Toxicity resolves to Grade 0-1	Toxicity does not resolve within 12 weeks of last dose or inability to reduce corticosteroid to 10 mg or less of prednisone or equivalent per day within 12 weeks.
	4	Permanently discontinue	Permanently discontinue
Hyperthyroidism	3	Toxicity resolves to Grade 0-1	Toxicity does not resolve within 12 weeks of last dose or inability to reduce corticosteroid to 10 mg or less of prednisone or equivalent per day within 12 weeks.
	4	Permanently discontinue	Permanently discontinue
Hypothyroidism	2-4	Therapy with pembrolizumab can be continued while treatment for the thyroid disorder is instituted	Therapy with pembrolizumab can be continued while treatment for the thyroid disorder is instituted.
Infusion Reaction	3-4	Permanently discontinue	Permanently discontinue
Pneumonitis	2	Toxicity resolves to Grade 0-1	Toxicity does not resolve within 12 weeks of last dose or inability to reduce corticosteroid to 10 mg or less of prednisone or equivalent per day within 12 weeks.
	3-4	Permanently discontinue	Permanently discontinue

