5.2.3.5 Radiotherapy Adverse Events

Adverse effects related to radiation therapy will be recorded. These include nausea/vomiting, diarrhea, poor appetite, weight loss, fatigue, skin erythema, esophagitis, carditis, pneumonitis, myelosuppression, myelitis, late pulmonary fibrosis, and esophageal stricture.

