7.1.5.3 Post-Treatment Visits

7.1.5.3.1 Safety Follow-Up Visit

The mandatory Safety Follow-Up Visit should be conducted approximately 30 days after the last dose of trial treatment or before the initiation of a new anti-cancer treatment, whichever comes first. All AEs that occur prior to the Safety Follow-Up Visit should be recorded. Subjects with an AE of Grade > 1 will be followed until the resolution of the AE to Grade 0-1 or until the beginning of a new anti-neoplastic therapy, whichever occurs first. SAEs that occur within 90 days of the end of treatment or before initiation of a new anti-cancer treatment should also be followed and recorded. Subjects who are eligible for retreatment with pembrolizumab (as described in [Section 7.1.5.5](#)) may have up to two safety follow-up visits, one after the Treatment Period and one after the Second Course Phase.

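### Late radiation effects are promised in the safety data, but for early-stopping patients new non-serious events have no clear collection route after about 30 days

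*Combined protocol and SAP*

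**What the plan says.** Section 5.2.3.5 commits the trial to recording radiation effects. Its list ends with "late pulmonary fibrosis, and esophageal stricture", and no period is given.

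Section 5.6 sets the general window: "After the end of treatment, each subject will be followed for 30 days for adverse event monitoring". The same sentence adds that "serious adverse events will be collected for 90 days after the end of treatment". Section 7.1.5.3.1 puts the safety visit "approximately 30 days after the last dose of trial treatment or before the initiation of a new anti-cancer treatment, whichever comes first" and says "All AEs that occur prior to the Safety Follow-Up Visit should be recorded". It also keeps existing events under follow-up: "Subjects with an AE of Grade > 1 will be followed until the resolution of the AE to Grade 0-1", or until new anti-neoplastic therapy begins.

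Patients who stop for a reason other than progression are seen every 6 weeks for imaging (7.1.5.4). After confirmed progression or new therapy, contact is a telephone call every 12 weeks about survival (7.1.5.4.1).

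Section 7.1.2.1 reads differently. It has adverse experiences graded and recorded for the whole study and in the follow-up period, and Section 7.1.4.1 uses that term for the phase after the safety visit.

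Section 4.2.1 gives the reason for looking: "safety should still be assessed in this early cohort of patients to ensure immune-mediated or radiation-induced toxicities are not exacerbated by the combination".

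**The concern.** The first secondary objective (3.2) is feasibility with an acceptable safety profile, and Section 9.1 makes acceptable toxicity part of what would count as a clear sign of promise. Late fibrosis and stricture are by name not early events, yet radiotherapy is over within about two weeks of C1D1 and the all-AE window normally runs from a pembrolizumab date. The earlier a patient stops, the sooner observation for late radiation effects ends. Such patients stay in the safety set, which needs only one dose of pembrolizumab (9.2).

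A low count of late radiation events could then reflect short observation rather than low toxicity. Because 7.1.2.1 conflicts with 5.6 and 7.1.5.3.1, staff could also collect differently from patient to patient, and a reader of the report could not tell which rule was followed.

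**Working it through.** The plan states no figure to reproduce; this is calendar arithmetic.

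Inputs:
- Radiotherapy: 10 weekday fractions from C1D1 (Table 1; calendar note e). With no holiday or delay, the last fraction falls on day 12 for a Monday start and day 14 for any other weekday.
- Pembrolizumab every 3 weeks (Table 1), so the day of dose n is 1 + 21(n - 1).
- All-AE window: last dose + 30 days (5.6, 7.1.5.3.1).
- SAE window: last dose + 90 days (5.6, 8.7.1.1).

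Days observed after radiotherapy = 1 + 21(n - 1) + window - radiotherapy end day. The range runs from end day 14 to end day 12.

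| Doses | Last dose, day | All-AE window closes, day | Days after RT, all AEs | Days after RT, SAEs |
|---|---|---|---|---|
| 1 | 1 | 31 | 17-19 | 77-79 |
| 2 | 22 | 52 | 38-40 | 98-100 |
| 3 | 43 | 73 | 59-61 | 119-121 |
| 4 | 64 | 94 | 80-82 | 140-142 |
| 5 | 85 | 115 | 101-103 | 161-163 |

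If the last fraction counts as the last trial treatment, the 1-dose row becomes 30 and 90 days. From 2 doses on nothing changes, because pembrolizumab is then the later treatment unless radiotherapy is delayed into cycle 2. New anti-cancer therapy shortens both windows.

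The documents give no onset time for late effects, so I take a range of L days after radiotherapy. The all-AE window reaches L when 21(n - 1) is at least L + end day - 31:
- L = 90: 71 to 73, divided by 21 = 3.4 to 3.5, so n = 5.
- L = 180: 161 to 163, divided by 21 = 7.7 to 7.8, so n = 9.
- L = 365: 346 to 348, divided by 21 = 16.5 to 16.6, so n = 18.

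For the 90-day SAE window, 91 replaces 31, and the minimum is 2, 6 and 15 doses.

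Who has 4 or fewer doses? The first scan is at week 6 (day 43) and a confirmatory scan comes 6 weeks later (day 85). A patient stopped at either, before any dose due that day, has had 2 or 4 doses.

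To illustrate what lost observation does in a trial of 14, the chance of seeing at least one case is 1 - (1 - p)^m, where m patients are observed long enough:
- p = 10% (assumed): 77% with m = 14, 52% with m = 7, 34% with m = 4.
- p = 20% (assumed): 96%, 79% and 59%.

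Neither p nor m comes from the documents.

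**The case against.** Several parts of the protocol narrow the gap.

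- Serious events: beyond the 90 days, Section 8.3 reports all SAEs on study under institutional policy, with no 90-day limit and no restriction to the Merck product. Section 8.7.1.1 adds an untimed route for SAEs judged related to that product. These texts do not fully agree with each other, but serious late events are not simply lost.
- Immune events: Section 5.2.1.2 warns that "These adverse events may occur shortly after the first dose or several months after the last dose of treatment", and a reader might infer that delayed immune toxicity is missed in the same way. The documents do not support that. Section 7.1.2.1 has possible immune events assessed as events of clinical interest, 8.7.1.1 handles non-serious ones like SAEs, and 5.3.1 continues concomitant-medication recording for them beyond 30 days. This part is largely covered.
- Existing events: esophagitis or pneumonitis above Grade 1 at the safety visit stays under follow-up until it resolves or new therapy begins. That does not pick up new onset.
- Section 7.1.2.1 can be read as continuing all AE recording. This stands as a contradiction to resolve; it does not show that collection continues. The calendar's AE-review row cannot settle it, because its columns are not reliable in the text available.
- The clock: 7.1.5.3.1 counts from trial treatment, and Table 1 lists radiotherapy as such. This changes only the 1-dose figure.
- Early progression need not end dosing. Clinically stable patients may continue to a confirmatory scan (Table 4), and a patient first progressing at week 12 may receive more than 4 doses.
- Fibrosis and stricture matter mainly for thoracic or esophageal fields, whereas 5.2.3.1 also allows gastric and metastatic targets. Some early stoppers will die before a late effect could appear, and for them the window loses nothing.

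What remains is the new-onset, non-serious event attributed to radiotherapy, mainly in a patient who has progressed or started other therapy.

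**Conclusion.** The point holds for late, non-serious radiation effects. Under 5.6 and 7.1.5.3.1, patients with 1 to 4 doses have from about 17 to 82 days of all-AE observation after radiotherapy, and at least 5, 9 or 18 doses are needed to reach an assumed onset at 90, 180 or 365 days. The day counts assume on-time dosing, no holidays and no new therapy within the window.

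A reader might infer that the combination will look safer than it is. The documents do not support that: they give no late-event rate, no onset time and no distribution of doses received, and there is no comparator. What can be said is that late radiation toxicity may be under-counted, by an unknown amount. A reader might also infer that the safety holds are weakened. They are not: the cycle 1 discontinuation rule and the treatment-related death rule in 9.2 do not depend on this window.

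**What to change.** Reconcile Sections 5.2.3.5, 5.6, 7.1.2.1, 7.1.5.3.1, 8.3 and 8.7.1.1 so that one statement says which events are collected, from whom and until when. Then:

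1. Keep the general 30-day and 90-day windows.
2. Give the late effects in 5.2.3.5 their own collection period. Record new events attributed to radiotherapy, at least pneumonitis or fibrosis and esophageal stricture, at the existing 6-weekly follow-up visits and 12-weekly survival calls, and note the start date of any new therapy.
3. Report late radiation events alongside each patient's observation time from the last fraction, so that a zero count can be read against how long patients were watched.

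No broader extension for immune events is needed. The cost is an amendment, one CRF page and a few questions at contacts already scheduled, with no added visits. The drawback is that attribution becomes less certain once new therapy has started; the recorded start date lets readers judge that.

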5.6.1 Discontinuation of Study Therapy after CR

Discontinuation of treatment may be considered for subjects who have attained a confirmed CR that have been treated for at least 24 weeks with pembrolizumab and had at least two treatments with pembrolizumab beyond the date when the initial CR was declared. Subjects who then experience radiographic disease progression may be eligible for up to one year of additional treatment with pembrolizumab via the Second Course Phase at the discretion of the investigator if no cancer treatment was administered since the last dose of pembrolizumab, the subject meets the safety parameters listed in the Inclusion/Exclusion criteria, and the trial is open. Subjects will resume therapy at the same dose and schedule at the time of initial discontinuation. Additional details are provided in [Section 7.1.5.5](#).

5.7 Clinical Criteria for Early Trial Termination

Early trial termination will be the result of the criteria specified below:

1. Quality or quantity of data recording is inaccurate or incomplete
2. Poor adherence to protocol and regulatory requirements
3. Incidence or severity of adverse drug reaction in this or other studies indicates a potential health hazard to subjects
4. Plans to modify or discontinue the development of the study drug

In the event of Merck decision to no longer supply study drug, ample notification will be provided so that appropriate adjustments to subject treatment can be made.

6.0 STUDY CALENDAR

6.1 Initial Treatment Phase

Trial Period:	Screening Phase	Treatment Cycles						End of Treatment	Post-Treatment			
		C1/D1	C1/D8	C1/D15	C2D1	C3D1	C4D1	C5D1	C6+D1 ^a	Last Dose	Safety Follow-up	Follow Up Visits ^b
Treatment Cycle:	Main Study Screening											
Scheduling Window (Days):	-21 to -1				± 1	± 1	± 3	± 3	± 3	At time of Discon	30 days post discon	Every 6 weeks post discon
Administrative Procedures												
Informed Consent	X											
Inclusion/Exclusion Criteria	X											
Demographics and Medical History	X											
Prior and Concomitant Medication Review	X	X	X	X	X	X	X	X	X	X	X	X
Post-study anticancer therapy status												
Survival Status												X
Clinical Procedures/Assessments												
Review Adverse Events		X	X	X	X	X	X	X	X	X	X	X
Full Physical Examination	X											X
Directed Physical Examination		X	X	X	X	X	X	X	X	X	X	X
Vital Signs and Weight	X	X	X	X	X	X	X	X	X	X	X	X
ECOG Performance Status ^d	X	X	X	X	X	X	X	X	X	X	X	X
Trial Treatment Administration												
Pembrolizumab		X	X	X	X	X	X	X	X	X	X	X
Palliative Radiotherapy ^e		X	X	X	X	X	X	X	X	X	X	X
Laboratory Procedures/Assessments: analysis performed by LOCAL laboratory												

Trial Period:	Screening Phase	Treatment Cycles						End of Treat ment	Post-Treatment				
		C1/D1	C1/D8	C1/D15	C2D1	C3D1	C4D1	C5D1	C6+D1 ^a	Last Dose	Safety Follow-up	Follow Up Visits ^b	Survival Follow-Up ^c
Treatment Cycle:	Main Study Screening												
Scheduling Window (Days):	-21 to -1												
Pregnancy Test – Urine or Serum β-HCG ^f	X												
PT/INR and aPTT ^d	X												
CBC with Differential ^d	X	X	X	X	X	X	X	X	X	X	X	X	
Comprehensive Serum Chemistry Panel ^d	X	X	X	X	X	X	X	X	X	X	X	X	
Urinalysis ^d	X												
T3, FT4 and TSH ^{d,g}	X						X			X ^g		X	
Serum carcinoembryonic antigen (CEA) ^h	X					X		X		X ^h			
12-Lead EKG	X												
Efficacy Measurements													
Tumor Imaging ⁱ	X					X		X	X ⁱ		X		
Tumor Biopsies/Correlative Studies Blood													
Tumor Biopsies ^j	X					X							
Correlative Studies Blood/Stool/Oral Swab Collection ^k	X					X				X			

Trial Period:	Screening Phase	Treatment Cycles						End of Treat ment	Post-Treatment					
		Main Study Screening	C1/D1	C1/D8	C1/D15	C2D1	C3D1	C4D1	C5D1	C6+D1 ^a	Last Dose	Safety Follow-up	Follow Up Visits ^b	Survival Follow-Up ^c
Treatment Cycle:														
Scheduling Window (Days):	-21 to -1				± 1	± 1	± 3	± 3	± 3	± 3	± 3	At time of discon	30 days post discon	Every 6 weeks post discon
a.	Patients will continue pembrolizumab for a maximum of 35 cycles for first course of therapy if no evidence of disease progression or intolerable toxicity.													
b.	In patients who discontinue study therapy without documented disease progression, every effort should be made to continue monitoring disease status by radiologic imaging every 6 weeks (± 7 days) until 1) the start of new anti-cancer treatment, 2) disease progression on imaging, 3) death, or 4) the end of the study, whichever occurs first.													
c.	After the start of new anti-cancer treatment or documented disease progression by imaging, the patient should be contacted by telephone every 12 weeks to assess for survival status.													
d.	Laboratory tests and ECOG PS are to be performed within 10 days prior to the first dose of trial treatment.													
e.	Palliative radiotherapy to a total dose of 30 Gy to the primary tumor will be delivered in 3 Gy fractions daily with the exception of weekends and holidays. The first fraction of radiation should be given on C1D1 prior to administration of pembrolizumab. Radiation may continue into cycle 2 if delayed for management of toxicity or administrative reasons.													
f.	For women of reproductive potential, a urine pregnancy test will be performed within 72 hours prior to the first dose of trial treatment. A serum test may be considered if urine test is not appropriate or inconclusive.													
g.	Thyroid function tests should be collected at screening and every 6 weeks in concordance with day 1 of even-numbered cycles.													
h.	Serum CEA should be collected at screening and every 6 weeks in concordance with day 1 of odd-numbered cycles.													
i.	Tumor imaging should be performed every 6 weeks through the first 6 cycles, then subsequently performed every 9 weeks thereafter. For patients who complete 35 cycles of therapy or 2 years of follow up without evidence of progression, scans can be spaced out to every 12-24 weeks at the discretion of the treating physician. The exception will be patients who demonstrate PD, PR, or CR by RECIST 1.1, in which event the next imaging will be performed at 6 weeks for confirmation. Refer to Section 7.1.2.6.2 for details.													
j.	Tumor biopsies will be performed prior to cycle 1/day 1, and at 21 days (± 3 days) after completion of palliative radiotherapy. Biopsies will be performed of metastatic sites amenable to access by CT or ultrasound-guidance. Malignant ascites accessible by ultrasound guidance will also be eligible as tumor biopsy specimens. For patients receiving RT to a metastatic site and only the primary tumor is accessible to biopsy, these will be obtained by endoscopy.													
k.	Blood/stool/oral swab collection for correlative studies will be collected at screening assessment, at 21 days (± 3 days) after completion of palliative radiotherapy, at timepoint of first progression by RECIST (if applicable and continued on protocol therapy), and at end of treatment.													

